5.1.1 Screening Period

Study procedures cannot be performed until subjects sign the informed consent form (ICF). Once subjects sign the ICF, they are considered “enrolled” in the study, and they enter the screening period. During the screening period, subjects will complete the study procedures and baseline assessments outlined in the Schedule of Activities (Section 2) to determine if they continue to meet eligibility criteria (Section 6).

To be eligible for the study, a subject must meet minimum disease activity criteria outlined in Section 6.1, including a modified Mayo score of 5 to 9 points, inclusive.

[REDACTED]

An endoscopy (colonoscopy or flexible sigmoidoscopy) will be performed to determine if a subject has active intestinal inflammation (assessed by central reading) and to obtain biopsies for biomarker [REDACTED] assessment. To avoid unnecessary endoscopies, best practice is to complete other screening investigations first and check the results of those investigations to confirm ongoing eligibility before a subject begins bowel preparation for endoscopy. **Subjects must be randomized within 14 calendar days of the screening endoscopy.**

NOTE: *In the case of rescreening, the 14-day window to be randomized following endoscopy may be extended an additional 3 days with approval of the BMS Medical Monitor/designee.*

A full colonoscopy will be required: (1) in subjects with a history of UC > 8 years, if endoscopy was not performed in the prior 12 months; or (2) in subjects who require a colonoscopy to screen or surveil for dysplasia, based on local guidelines; or (3) in subjects who require a colonoscopy to screen for colorectal carcinoma, based on local guidelines.

A full colonoscopy is encouraged if disease extent is unknown in order to define the proximal extent of colitis.

To be eligible for randomization, subjects must meet the Inclusion Criteria outlined in [Section 6.1](#) and must not meet any of the Exclusion Criteria outlined in [Section 6.2](#). Subjects must have had an inadequate response, loss of response, or intolerance to a treatment course of 1 or more of the standard medications for UC and completed at least 1 treatment course of corticosteroids (Section 6.1). Detailed criteria defining inadequate response, loss of response, or intolerance to biologic therapy are described in [APPENDIX 5](#). The prior medication failure or intolerance used to qualify a subject for inclusion must be recorded in source documents and the appropriate eCRF.

Prohibited treatments are listed in [Section 7.7.1 \(Table 6\)](#).

Restricted treatments are listed in [Section 7.7.2 \(Table 7\)](#).

Dose stabilization rules are outlined in Section 0 ([Table 8](#)). Briefly, 5-aminosalicylic acids (5-ASAs) and oral corticosteroids (prednisone \leq 20 mg QD PO or equivalent or budesonide \leq 9 mg QD PO Multi-Matrix System [MMX[®]] colonic-delivery technology; eg, Uceris[®] or equivalent) are allowed, subject to dose stabilization rules. Equivalent doses of common corticosteroids are listed in [APPENDIX 6](#).

Washout periods for immunomodulators and biologic medications are outlined in the eligibility criteria ([Section 6](#)) and Table 6, and detailed in [APPENDIX 7](#). Subjects must comply with these washout periods in order to be eligible to be randomized. [REDACTED] assays that test for drug levels of some biologic medications are commercially available in many countries for use in routine clinical practice. They are also available as an optional test during the screening period. The washout period for these biologics can be waived in subjects who have an undetectable drug level [REDACTED] that is performed either in routine clinical practice or during the screening period.

██████████ used to waive the washout period as described above, the result ██████████ must be available in source documents, and the subject cannot receive another dose of that biologic prior to randomization.

Investigators are also encouraged to confirm if screening for noncolorectal malignancy is up to date prior to randomization, according to local guidelines (eg, screening for breast cancer or cervical carcinoma in situ).

5.1.2 Double-blind Treatment Period

At the Day 1 study visit, subjects who have completed the screening procedures and meet the eligibility criteria will be randomized in a 3:1 ratio to receive BMS-986165 12 mg BID or placebo BID PO, respectively for the 12-week double-blind treatment period. Randomization criteria are outlined in [Section 6.3](#). Subjects randomized to the 6 mg BID arm under the Original Protocol or Protocol Amendment 01 will continue to receive 6 mg BID for the 12-week double-blind treatment period and will receive 6 mg BID in the OLE period.

Prior to each scheduled visit, the subject diary should be reviewed to ensure SF and RB data have been entered daily. Prior to each scheduled visit at which Mayo scores are to be calculated, study personnel should ascertain whether an adequate number of days of diary entries have been made ([APPENDIX 9](#)). If adequate entries have not been made, the site should contact the subject to reschedule the visit to allow time for a sufficient number of daily diary entries for endpoint assessment, and the subject should be counseled about proper study procedures.

Endoscopy for the assessment of efficacy at Week 12 must occur in a window of 7 days prior to the Week 12 visit.

If a colonoscopy is performed during the screening visit, colonoscopy will be the preferred endoscopic procedure for subsequent endoscopies within the study. This approach will facilitate comparison between the individual colonic segments assessed at the screening visit and subsequent assessments.

Treatment discontinuation criteria are detailed in [Section 8.1](#). Subjects who **temporarily interrupt study treatment** will remain in the study and continue to participate in study procedures ([Section 8.1.1](#)).

Subjects who **permanently discontinue study treatment** will complete an **ET visit**. For subjects who permanently discontinue study treatment between Weeks 4 and 12, the ET visit will include an endoscopy. For subjects who permanently discontinue study treatment prior to Week 4, endoscopy at the ET visit is optional but encouraged. Subjects who permanently discontinue study treatment will be followed for protocol-specified posttreatment follow-up procedures. The only exception to this is when a subject specifically withdraws consent for any further contact with him/her or with persons previously authorized by the subject to provide this information (see [Section 8.2](#)).

5.1.3 Open-label Extension Period

Subjects who are likely to derive a clinical benefit from ongoing participation in the study following Week 12, as judged by the investigator, are eligible to enter the OLE period. The OLE

period will last up to 40 weeks, to Week 52. Subjects will receive BMS-986165 6 mg BID PO during the OLE. There is no provision for dose escalation of IP during the OLE.

[REDACTED]

[REDACTED]

[REDACTED]

The symptomatic Mayo score at the Week 20 visit will be calculated using the **3 most recent (not necessarily consecutive) valid electronic subject diary entries recorded from the 7 days prior to the day of the study visit.**

[REDACTED]

Subjects who require any rescue therapy during the OLE period (Section 5.1.5) must permanently discontinue from study treatment (Section 8.1).

Endoscopy for the assessment of efficacy at Week 52 must occur in a window of 7 days prior to the Week 52 visit.

Endoscopy is required at the ET visit for subjects who permanently discontinue study treatment between Week 20 and prior to Week 52. Endoscopy is optional, but encouraged, for subjects who have an ET visit between Weeks 12 and 20.

5.1.4 Follow-up Period

Subjects who complete the Week 12 visit and decline to enter the OLE period, those who complete the Week 52 visit and do not roll-over into a long-term extension study, or those who permanently discontinue study drug at any time during the study ([Section 8](#)) will enter a 4-week posttreatment follow-up period.

5.1.5 Treatment Failure

For the purpose of this study, treatment failure will be defined as:

[REDACTED]

[REDACTED]

[REDACTED]

5.1.6 Safety Monitoring and Data Monitoring Committee

Study IM011127 is the first experience of subjects with moderate to severe UC to BMS-986165 at doses above 6 mg BID PO. Consequently, this study has been designed to closely monitor subjects' safety throughout the duration of the study. Safety monitoring will occur at study sites, by the Sponsor, and by an external, independent DMC.

Subject Safety Assessments at the Study Site

Subject safety will be closely assessed at study sites by the investigator and appropriately delegated members of the study team. The assessments outlined in the Schedule of Activities (see [Section 2](#)) have been designed to facilitate assessment of safety in addition to efficacy. Based on the timing of hepatic AEs observed [REDACTED], liver function testing during the treatment phase will commence at Week 1 (~Day 8) ([Table 1](#)). In addition, the Sponsor has implemented additional data collection for AEs, including skin SOC TEAEs (see [Section 9.2.8](#)), in order to more completely characterize these TEAEs (were they to occur) and understand the tolerability of BMS-986165 in this study.

Additional clinical assessments or investigations can be performed during the study as indicated, based on the judgment of the investigator.

Medical Monitoring by the Sponsor

Subject safety will be monitored in a blinded manner by the Sponsor on a regular basis. The Sponsor will review blinded subject-level data entered in the clinical database as well as aggregated safety data across studies. This approach facilitates close monitoring of individual safety events as well as surveillance for potential safety signals.

Data Monitoring Committee

An external, independent DMC will provide oversight on the safety of trial subjects within this study. The DMC will regularly review accumulating data from this study and advise the Sponsor

regarding the continuing safety of trial subjects and those yet to be recruited to the trial, as well as the continuing validity and scientific merit of the trial.

Data summaries and listings will be provided to the DMC to facilitate their safety assessment at regularly scheduled meetings and on an ad hoc basis if needed. Efficacy data will be made available on request by the DMC to assess ongoing acceptability of the benefit-risk profile. The DMC will also be provided with suspected, unexpected serious adverse reaction (SUSAR) reports relating to BMS-986165 and recommendations from other DMCs supporting the BMS-986165 clinical development program.

Regular DMC safety reviews will include all AEs, SAEs, and AEs of special interest. Based on their review of safety data, the DMC will make recommendations regarding the appropriateness of continuing the study, with or without study modifications, or stopping the study.

In addition to regularly scheduled DMC meetings, ad hoc DMC meetings will occur in the following circumstances:

- Two or more subjects experience an SAE of the same PT and that is considered related to the study treatment by the investigator (for example, not explained by intercurrent medical condition or concomitant medication)
- Two or more subjects are discontinued due to the same laboratory abnormality as defined by criteria in [Section 8.1](#)

Additional details on the DMC's processes and procedures will be outlined in the DMC Charter.

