AE = adverse event; [REDACTED] BP = blood pressure; COVID-19 = Coronavirus Disease 2019; CXR = chest x-ray; [REDACTED] ECG = electrocardiogram; eCOA = electronic clinical outcome assessments; FACS = fluorescence-activated cell sorting; [REDACTED] HBsAg = hepatitis B surface antigen; [REDACTED] HR = heart rate; hsCRP = high-sensitivity C-reactive protein; IBDQ = Inflammatory Bowel Disease Questionnaire; ICF = informed consent form; [REDACTED] IP = investigational product; IRT = interactive response technology; N/A = not applicable; OLE = open-label extension; PBMC = peripheral blood mononuclear cells; PCR = polymerase chain reaction; PGA = Physician's Global Assessment; [REDACTED] SAE = serious adverse event; SARS-CoV-2 = Severe Acute Respiratory Syndrome Coronavirus 2; [REDACTED] SF = stool frequency; [REDACTED] Temp = temperature; TSH = thyroid-stimulating hormone; UC = ulcerative colitis; WOCBP = women of childbearing potential

^b FSH may be performed in amenorrheic females < 55 years of age if indicated to confirm postmenopausal status (see APPENDIX 4). It will not be considered a protocol deviation if a site obtains an FSH level in error, ie, in male subjects.

- d Diagnostic testing for SARS-CoV-2 infection should be performed as close as possible to randomization and must be confirmed as “negative” prior to randomization.
- e A multipathogen molecular panel for enteric pathogens (eg, multipathogen PCR) may be considered as an alternative to stool culture, if this is routinely performed at a site and its use is consistent with local standard of care. Use of this test within the study should be discussed with the BMS Medical Monitor/designee.
- f Efficacy instruments listed in italics are for site reference only. **These scores will not be calculated by the investigator.**
- g A CXR performed less than 6 months prior to signing of the ICF may be used in place of the screening CXR, provided the subject has no symptoms or signs suggestive of pulmonary disease in the interim.
- h Chemistry only (liver function test panel).
█
█
█
- i To be collected only from those subjects who sign the appropriate consent form.
- m It will not be considered a protocol deviation if a subject is unable to produce a stool sample at Day 1, provided that █ fecal lactoferrin have been successfully collected at the screening visit.
- n The modified Mayo score calculated to determine eligibility will be used for randomization on Day 1 as the baseline score.

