- o IP will be dispensed only to those subjects who continue in the study and enter the OLE period ([Table 2](#)).
- p AEs related to COVID-19 should be collected from time of signing informed consent.

General procedural note: The protocol does not mandate specific investigations at unscheduled visits. Unscheduled visit study procedures should be based on the clinical judgment of the investigator.

Table 2: Open-label Extension Period Procedural Outline (IM011127)

Study Procedure	Week 16 (Day 113)	Week 20 (Day 141)	Week 24 (Day 169)	Week 32 (Day 225)	Week 40 (Day 281)	Week 52 (Day 365) EOT/ET ^d	Week 56 (Day 393) F/U	Notes
Visit window (± n days)	3	3	3	3	3	3	7	
Disease Assessments								
Concomitant medications and UC medications	X	X	X	X	X	X	X	Section 7.7 and APPENDIX 7
Tobacco/e-cigarette use	X	X	X	X	X	X	X	Section 6.4
Physical Examination								Section 9.4.1
Physical examination	X	X	X	X	X	X	X	Section 9.4.1
Weight						X	X	Section 9.4.1
Vital signs (HR, BP, Temp)	X	X	X	X	X	X	X	Section 9.4.5
Electronic Diary (eCOA Device)								Section 9.1.1
Subject completes electronic daily diary	X					X		APPENDIX 9
Review compliance with electronic daily diary	X	X	X	X	X	X		APPENDIX 9
ECG								
ECG			X			X	X ^e	Section 9.4.6
Blood and Urine Tests								
Hematology, chemistry, coagulation	X	X	X	X	X	X	X	Section 9.4.3 and Table 11
Fasting lipid panel and glucose			X			X		Section 9.4.3 and Table 11

Table 2: Open-label Extension Period Procedural Outline (IM011127)

Study Procedure	Week 16 (Day 113)	Week 20 (Day 141)	Week 24 (Day 169)	Week 32 (Day 225)	Week 40 (Day 281)	Week 52 (Day 365) EOT/ET ^d	Week 56 (Day 393) F/U	Notes
Visit window (± n days)	3	3	3	3	3	3	7	
Serum hsCRP	■	■	■	■	■	■		■
Urinalysis and urine chemistry						X		Section 9.4.3 and Table 11
Additional Blood Tests ■								
Whole blood for gene expression	X		X			X		Section 9.6 and Table 13
Stool Collection								Aliquots from single sample
Stool for fecal lactoferrin	X	X	X	X	X	X	X	Section 9.6 and Table 13
Endoscopy and Endoscopic Biopsies								
Endoscopy						X		Section 9.1.1

Table 2: Open-label Extension Period Procedural Outline (IM011127)

Study Procedure	Week 16 (Day 113)	Week 20 (Day 141)	Week 24 (Day 169)	Week 32 (Day 225)	Week 40 (Day 281)	Week 52 (Day 365) EOT/ET ^d	Week 56 (Day 393) F/U	Notes
Visit window (± n days)	3	3	3	3	3	3	7	
Biopsies for gene expression						X		Section 9.6 and Table 14
Biopsies from noninvolved area (if available) for gene expression						X		Section 9.6 and Table 14

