10.4.2.3 Clinical Laboratory Tests

Laboratory analytes will be summarized as raw, change from baseline, including the maximum postbaseline value. Incidence of abnormal, high, or low values will be summarized. Shift tables will also be provided. Baseline values are defined as the last nonmissing value prior to the first dose of study drug. The number and proportion of subjects with clinical laboratory abnormalities will be summarized at each scheduled visit.

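### With one safety baseline for all periods, former placebo subjects' open-label changes start before placebo rather than before their first BMS-986165 dose

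*Combined protocol and SAP*

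**What the plan says.** **Baseline.** Section 10.4.2.3 (laboratory tests) states: "Baseline values are defined as the last nonmissing value prior to the first dose of study drug". Section 10.4.2.2 applies the same rule to vital signs and ECGs. Section 10.4.1 gives efficacy a similar rule but allows exceptions where indicated; the two safety sections have no such allowance. Section 10.4.2 asks for safety data by period and also combined. Sections 10.4.2.2 and 10.4.2.3 call for raw values, change from baseline, the maximum post-baseline value and abnormality counts per visit. Section 10.4.2.3 adds shift tables.

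**Treatment.** Section 7 lists both BMS-986165 and placebo as study treatments. Section 10.1 plans about 13 placebo subjects. Section 5.1.3 states: "Subjects will receive BMS-986165 6 mg BID PO during the OLE". Footnote o of Table 1 places the first OLE dispensing at Week 12: "IP will be dispensed only to those subjects who continue in the study and enter the OLE period".

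**Liver tests.** Section 5.1.6 gives its reason as "Based on the timing of hepatic AEs observed", followed by a redaction, and concludes that "liver function testing during the treatment phase will commence at Week 1 (~Day 8"), citing Table 1. Table 2, which covers the OLE, has its first visit and first chemistry sample at Week 16.

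**The concern.** The baseline rule does different things in different arms. For a subject on 12 mg BID, or one of the few on 6 mg BID, the Day 1 value is the last one before any BMS-986165. For a placebo subject, the last value before any BMS-986165 is the Week 12 value, which the rule passes over. Former placebo subjects are the only people who meet the drug for the first time in the OLE. Their change-from-baseline and shift outputs are therefore where a reader would look for the effect of starting at the OLE dose.

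Measured from before placebo, those outputs combine 12 weeks of change on placebo, including the course of the colitis itself, with change on drug. A rise during placebo would appear as an OLE shift. A fall during placebo could offset a rise on drug.

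**Working it through.** **The plan's own safety figures.** Section 10.1.2 gives 98% and 90% as the chance of seeing at least one event in 37 subjects at 10% and 6% incidence. Both reproduce: 1 − 0.90^37 = 0.980 and 1 − 0.94^37 = 0.899. They concern the 12 mg arm and are not in question here.

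**What the rule means for a placebo subject.** Study drug is not formally defined, so the reading has to be argued.
1. Section 7 makes placebo a study treatment.
2. Section 5.1.4 uses study drug for treatment stopped at any time during the study, which includes the blinded period.
3. If study drug meant BMS-986165 only, a placebo subject who never entered the OLE would have no baseline. One who did enter would have a Week 12 baseline for the double-blind period as well. Neither can be intended.

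The natural reading is therefore the pre-placebo value.

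**Spans.** Inputs are the nominal days in Tables 1 and 2: first blinded dose on Day 1, Week 12 on Day 85, Week 16 on Day 113. Time on placebo is 85 − 1 = 84 days. For an OLE visit on day *d*, the span from the Day 1 value is *d* − 1 and time on BMS-986165 is *d* − 85.

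| OLE visit | Days since Day 1 | Days on BMS-986165 | Share of span on placebo |
|---|---|---|---|
| Week 16 (Day 113) | 112 | 28 | 84/112 = 75% |
| Week 24 (Day 169) | 168 | 84 | 84/168 = 50% |
| Week 52 (Day 365) | 364 | 280 | 84/364 = 23% |

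The change at Week 16 splits exactly:

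Week 16 − Day 1 = (Week 12 − Day 1) + (Week 16 − Week 12).

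The first bracket is change on placebo and the second is change on drug. The present rule reports the sum; only the second bracket bears on first exposure. The maximum post-baseline value has a related difficulty: in the combined-period summary, a placebo subject's maximum may come from the placebo weeks.

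**Is the better reference available?** Table 1 schedules chemistry, hematology, coagulation, vital signs and an ECG at Week 12. For ECGs the gap is wider: there is none on Day 1, so the pre-placebo reference is the screening ECG. The first OLE ECG is at Week 24, more than 168 days after that reference.

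**Number affected.** At most about 13. If 70% to 100% enter the OLE (an assumption; the documents give no rate), 13 × 0.7 = 9.1, so about 9 to 13.

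**Liver-test schedule.** After the first blinded dose, chemistry falls at 8 − 1 = 7, 15 − 1 = 14 and 29 − 1 = 28 days: three scheduled tests. After first BMS-986165 in a former placebo subject, it falls at 113 − 85 = 28 days: one scheduled test. With ±3-day windows at both visits, the gap is 22 to 34 days.

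**The case against.** **On the baseline.** Three points can be made against it.
- Section 10.4 leaves detail to a SAP, which could add an OLE baseline. That is so, but Section 10.4.2.3 states its rule without exception, and nothing in the document modifies it.
- Study drug is undefined. That also stands, but the alternative reading fails for the placebo arm, as shown above.
- Many outputs need no baseline: raw values, abnormality counts per visit, and the liver criteria in Sections 8.1 and 9.2.7, which rest mainly on multiples of the upper limit of normal. This stands in full and limits the importance of the point. The effect is confined to outputs that use a baseline, in a descriptive analysis.

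**On the liver tests.** A reader might infer that the protocol contradicts itself, or that a hepatic signal in former placebo subjects would be missed. The documents do not support either.
- Section 5.1.6 cites only Table 1, which covers screening and the double-blind period.
- The source and dose of the hepatic events are redacted. The section opens by referring to doses above 6 mg BID, while the OLE dose is 6 mg BID. The comparison of three tests with one is therefore partly a comparison of doses.
- Only scheduled tests are absent between Weeks 12 and 16. Chemistry is taken at both ends, and investigators may test at other times.
- No hepatic event rate is given from which to judge consequence.

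What remains is that Section 5.1.6 speaks of the treatment phase without naming a dose, and does not say whether its reasoning applies when a former placebo subject first takes the drug.

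**Conclusion.** The baseline point holds. As written, OLE change and shift results for about 13 former placebo subjects at most (9 to 13 if 70% to 100% enter) would be measured from before placebo. At Week 16, 84 of the 112 days would be on placebo; the share falls to 23% by Week 52. This rests on reading study drug to include placebo and on nominal visit days. It is a modest defect in descriptive safety output, worth correcting because the correction is free. It does not affect the primary endpoint, the sample-size statements or any safety output that needs no baseline.

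The liver-test point is secondary. The 28-day interval is real, but it is an unexplained difference between two schedules. Nothing here shows that the OLE schedule is wrong.

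**What to change.** 1. In Sections 10.4.2.2 and 10.4.2.3, and in the SAP, add a rule for OLE summaries of subjects randomised to placebo. Baseline is the last nonmissing value before the first BMS-986165 dose, normally the Week 12 value. Change, maximum post-baseline change and shifts are computed from it. Keep the present rule for the double-blind period and for subjects randomised to BMS-986165, and state in each OLE table which baseline was used.
2. Reconcile Section 5.1.6 with Table 2 by stating whether the early liver-testing rationale extends to first exposure in the OLE. No testing schedule is proposed here.

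The first change costs wording and programming only. It needs no new sample, visit or data. The second calls for a sponsor statement; any clinical consequence is for the sponsor to decide.
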